Design: The study will use a between-subjects design to test two measures of reward (subjective effects and drug choice) in participants pre-selected based on their performance on the stop task (Logan et al., 1997), a standardized measure of impulsive action. Participants will be eligible to participate if they score in the upper (stop reaction time > 325ms; N=30) or lower (stop reaction time < 270ms; N=30) quartiles on stop task performance (calculated from over 500 previous subjects in our lab) during the screening session. Subjects will then participate in a 5-session choice procedure, consisting of 4 sampling sessions and one choice session. During the sampling sessions, participants will consume beverages containing 0.8 g/kg ethanol (divided into 4 servings of 0.2 g/kg each) or a matching placebo under double blind conditions. During the choice session, they will choose the beverage they prefer, and drink the number of servings (from 1-4) they prefer. The primary outcome measures are subjective ratings of stimulation, drug liking, "euphoria", and "arousal" (see below) on the sampling sessions, and choice and number of servings of alcohol or placebo on the choice session.

Participants: Healthy male and female volunteers, aged 21-29, will be recruited by posters, advertisements, and word-of-mouth referrals. Participants will provide consent under Protocol #13681B to undergo the screening procedure, which will include an EKG, physical exam, clinical psychiatric interview, and stop task performance. Participants will be moderate drinkers (7-30 drinks per week) who report at least one binge drinking episode (5 or more drinks on a single occasion for men; 4 for women) in the last month. Asian subjects who report a pronounced 'flushing' reaction will be excluded. Subjects who smoke >5 cigarettes/day will be excluded to avoid acute nicotine effects or withdrawal during the sessions. Additional exclusion criteria include any serious medical problems, Axis I psychiatric disorders including substance dependence (APA, 1994), pregnancy or lactation (females), lack of a high school education, and lack of fluency in English. Women not currently using hormonal contraceptives will only be tested during the follicular phase (days 1-14; White et al., 2002). We will monitor participant

characteristics throughout the study to ensure that the high and low impulsive groups are matched on sex, race, education, SES, alcohol drinking, cigarette smoking, and other drug use.

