Orientation Session: Subjects will attend an orientation session during which study procedures are explained, and trait impulsive action is re-assessed. They will read and sign the consent form, complete self-report questionnaire measures of personality, and perform the stop task. Subjects will also perform additional behavioral impulsivity tasks, including a go/no-go task and a delay discounting task, to determine the specificity of these effects to impulsive action and the stop task. Finally, they will complete a sweet taste test to examine associations between alcohol reward and a non-drug reward.

Sampling Sessions: During the four sampling sessions, subjects will undergo the pre-session screening procedures described above, and then on each of four sessions they will receive 4 color-coded beverages in green or blue cups, containing alcohol (0.2 g/kg per dose, total dose

0.8 g/kg) or placebo. Within each session all the beverages will contain either alcohol or placebo, and the alcohol or placebo sessions will be scheduled in alternating order, with the initial drug randomized. For each subject the alcohol beverages will be in cups of one color, and the placebo in cups of the other color. Alcohol and placebo color-coding will be randomized across subjects. Subjects will be told that the drug and dose in each color will be the same on both days, and instructed to pay close attention to the color of the beverage container and to associate the color with how the drug makes them feel.

Choice Session: During the choice session, subjects will undergo pre-session screening and then complete an alcohol purchase task in which they choose between varying amounts of money and each color cup. The subject will then choose the color of the beverage cup they prefer (i.e., green or blue) to ingest and the number of servings they would like to consume (1-4). Mood and physiological measures will be obtained at regular intervals but the primary outcome measures will be whether they choose alcohol over the placebo, and the number of servings they choose to drink.

Measures:

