Statistical analyses: First, we will check that the high and low impulsive groups are matched on sex, race, education, SES, cigarette smoking, alcohol drinking and other drug use. To test the hypothesis that individuals high in impulsive action will report significantly greater stimulation and euphoria after alcohol than those low in impulsive action, we will conduct 2 (Group) X 2 (Drug) mixed design analyses of variance (ANOVA), with dose order and sex included as covariates, for each of the subjective response measures (i.e., BAES, ARCI, and DEQ). Group (high or low impulsive action) will be the between-subjects factor, and will be determined at the orientation session (see above). The dependent measures of subjective stimulation and

euphoria will be calculated as area under the curve (AUC). An average AUC across the two alcohol sessions will be calculated, and an average AUC across the two placebo sessions will be calculated. If the overall F-test for the group X drug interaction is significant ($p < .05$), post hoc paired t-tests will be used to test for drug effects (relative to placebo) in the high and low impulsive action groups separately. To test the hypothesis that high impulsive individuals will exhibit greater preference for alcohol over placebo compared to low impulsive individuals, we will compare choice for alcohol or placebo in high and low impulsive individuals. We will perform a chi-square analysis to determine if the high impulsive action group is comprised of a higher number of choosers compared to the low impulsive action group, and a between-groups t test to see if the high impulsive action group chooses a greater number of alcohol servings than the low impulsive action group.

Sample size determination: Estimations of sample size were derived from our preliminary data with d-amphetamine. Between groups (high vs. low impulsive action) t tests for subjective response measures of Elation and Vigor (AUC; 20 mg vs. placebo) suggest a medium effect size ($d = .60\text{--}.68$). $N=60$ subjects would provide 80% power ($\alpha = .05$) to detect a difference between high and low impulsive individuals.

HUMAN SUBJECTS

Risks to subjects:

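### The unrestricted 80% power claim rests on a t test of mood AUC and gives no basis for the primary alcohol-choice chi-square; no two-sided calculation tried reaches 80% for choice, and neither does the t test itself.

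*Combined protocol and SAP*

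**What the plan says.** Under Design, the protocol plans two groups of 30, defined by "stop reaction time > 325ms; N=30) or lower (stop reaction time < 270ms; N=30" on the stop task. It lists choice and number of servings among the primary outcomes, beside the subjective ratings. Choice Session repeats that "the primary outcome measures will be whether they choose alcohol over the placebo, and the number of servings they choose to drink".

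Statistical analyses tests the subjective AUCs by a 2 (group) x 2 (drug) mixed ANOVA, with follow-up tests "If the overall F-test for the group X drug interaction is significant ($p < .05". Binary choice is tested separately: "We will perform a chi-square analysis to determine if the high impulsive action group is comprised of a higher number of choosers". Number of servings has its own between-groups t test.

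Sample size determination contains the only sizing argument. Its source is preliminary d-amphetamine data: "Between groups (high vs. low impulsive action) t tests for subjective response measures of Elation and Vigor (AUC; 20 mg vs. placebo", which "suggest a medium effect size ($d = .60\text{--}.68". It concludes that N=60 "subjects would provide 80% power ($\alpha = .05$) to detect a difference between high and low impulsive individuals". It does not state sidedness, expected choice rates or an effect size for a proportion.

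**The concern.** The power sentence follows a calculation for one kind of outcome but is worded as if it covered any difference between the groups. A yes/no answer given once per subject usually carries less information than a continuous score, so power worked out for an AUC cannot be carried over to a chi-square on choice.

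Choice bears directly on the preference half of the working hypothesis. A reader who relied on 80% could take a non-significant chi-square as fair evidence that the groups prefer alcohol equally. If the subjective ratings differed as well, the same reader might conclude that high-impulsive people are more sensitive to alcohol without preferring it more. With low power, neither inference is safe.

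**Working it through.** **Inputs from the protocol.** 30 per group (Design); alpha .05, d = .60 to .68 and stated power 80% (Sample size determination). No dropout allowance is stated, so none is applied.

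**Step 1: the plan's own figure.** For a two-sample t test with n per group, the noncentrality is d × √(n/2) = d × √15 on 58 df. This gives 2.32 at d = .60 and 2.63 at d = .68.

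| d | two-sided power | one-sided power |
|---|---|---|
| .60 | 62.8% | 74.3% |
| .65 | 69.7% | 80.0% |
| .68 | 73.6% | 83.1% |

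The 80% appears only one-sided, near d = .65. The planned group x drug F-test has one numerator df. It is equivalent to a two-sided t test on the alcohol-minus-placebo difference, so the two-sided column applies. Allowing for the two covariates (56 error df) gives 62.7–73.5%. At N=60 the smallest d with 80% two-sided power is 0.74.

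**Step 2: the chi-square.** The documents give no choice rates and no way to turn d into a difference in proportions. Both must be assumed. Three conversions from the low-group rate p_L to the high-group rate p_H were tried:

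- latent normal: p_H = Φ(Φ⁻¹(p_L) + d)
- latent logistic: logit p_H = logit p_L + dπ/√3
- Cohen's h: 2 arcsin√p_H − 2 arcsin√p_L = d

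Power is the sum of the probabilities of all 31 x 31 pairs of counts from two Binomial(30) groups for which the uncorrected Pearson chi-square gives p < .05, two-sided. Each cell shows d = .60 / d = .68.

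| p_L | latent normal | logistic | Cohen's h |
|---|---|---|---|
| 30% | 44.3 / 54.4% | 53.8 / 64.9% | 64.4 / 75.5% |
| 40% | 45.9 / 55.4% | 55.1 / 65.1% | 64.5 / 75.1% |
| 50% | 43.3 / 52.3% | 51.0 / 60.3% | 63.1 / 74.1% |
| 60% | 40.5 / 49.0% | 45.7 / 54.2% | 63.4 / 74.2% |
| 70% | 35.7 / 42.9% | 37.5 / 44.5% | 62.9 / 74.2% |

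The most favourable rate gives 45.9 / 55.6% (normal), about 66% at d = .68 (logistic) and 64.8 / 75.6% (h). With continuity correction, the latent-normal ranges over these rates fall to 25–36% and 31–45%. Widening p_L to 10–80%, with or without continuity correction, stretches the two latent-scale conversions to about 15–66%.

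**Step 3: one-sided check.** Rejecting when z > 1.645, the best case is 66% (latent normal) and 75% (logistic), both at d = .68. With d read as h and rates symmetric about 50%, it is 74% at .60, 80.1% at .65 and 83% at .68.

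**Step 4: what 30 per group can detect.** This step does not use d. Solving for p_H at 80% power (two-sided, uncorrected):

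| p_L | p_H needed | difference |
|---|---|---|
| 30% | 65.1% | 35 points |
| 40% | 74.9% | 35 points |
| 50% | 83.3% | 33 points |
| 60% | 90.1% | 30 points |
| 70% | 95.4% | 25 points |

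**The case against.** The strongest reply is that the power sentence directly follows the AUC t tests and is naturally read as referring to them. On that reading the protocol omits a power statement for choice but does not misstate one. This largely stands. A reader might infer that the protocol promises 80% for the chi-square and is contradicted by a true value of 36–56%. The documents support neither half: the sentence names no outcome, and 36–56% depends on a latent-normal conversion and on base rates that the protocol does not give. Nothing links an amphetamine mood effect to a shift in beverage choice.

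A reader might also infer that choice falls short of 80% on every reading. It does not: one-sided, with d taken as h, power is 80% at .65 and 83% at .68. That combines two favourable readings, and a standard 2x2 chi-square is non-directional although the hypothesis is directional. The supportable statement is limited to two-sided tests.

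Nor does the preference hypothesis rest on the chi-square alone. Number of servings is a separate primary choice measure with its own t test, and the purchase task is secondary. Finally, the protocol nowhere says that a null chi-square will be read as equal preference; that is a risk for readers, not a planned inference.

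What the reply leaves untouched is that a primary binary outcome has no sizing, and that the 80% does not hold two-sided even for the AUC test it comes from.

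**Conclusion.** The point holds in limited form. An unrestricted power figure is attached to a study with a primary binary outcome that the calculation does not address. The documents do not determine the chi-square's power. Under the assumptions stated in the working, every two-sided calculation tried at 30 per group is below 80%: from about 36% under the least favourable latent-normal setting to 76% under the most favourable reading as h, for low-group rates of 30–70% without continuity correction.

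Part of the shortfall is not specific to choice. The AUC t test gives 63–74% two-sided, so 80% is not a sound benchmark for either outcome. No single detectable difference covers all base rates: 33–35 points serves for low-group rates of 30–50%, but the figure is about 30 points at 60% and 25 at 70%. The conclusion concerns binary choice and the wording of the power sentence; it makes no claim about the power of the servings comparison.

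**What to change.** 1. In Sample size determination, limit the power sentence to the subjective AUC measures and state its sidedness: at 30 per group and two-sided .05, power is 63% at d = .60 and 74% at d = .68.
2. Add a line for choice, such as: with 30 per group, 80% power (two-sided .05, uncorrected chi-square) requires about 30% v 65%, 40% v 75%, 50% v 83%, 60% v 90% or 70% v 95% choosing alcohol. If a power figure derived from d is also given, label it as resting on an assumed conversion and name the base rates used.
3. In Statistical analyses, report the between-group difference in the proportion choosing alcohol with its 95% CI, and state that a non-significant chi-square will not be read as equal preference. With both rates near 50% the interval's half-width is about 1.96 × √(2 × 0.25/30) = 0.25, or 25 points, which shows how little a null result would exclude.

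The cost is a few sentences and one confidence interval, with no change to N or procedures. The downside is that the stated power becomes less favourable for both the AUC measures and choice.
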